10.4 PATIENT REPORTED OUTCOMES

10.4.1 Psoriasis Symptom Scale (PSS)

The PSS will be self-administered by the patient at visits indicated in the [Flow Chart](#).

The PSS is a four-item patient reported outcome (PRO) instrument that assesses the severity of psoriasis symptoms in patients with moderate to severe psoriasis. The symptoms included are: pain, redness, itching and burning from psoriasis. Current symptom severity is assessed as a daily diary, using a 5-point Likert-type scale ranging from 0 (none) to 4 (very severe). The PSS was developed based on published evidence supporting the development of two similar, proprietary patient-reported outcome instruments: the Psoriasis Symptom Inventory and the Psoriasis Symptom Diary. These measures were developed in accordance with FDA PRO Guidance and have published evidence of reliability, validity, and ability to detect change ([R14-3562](#), [R14-3559](#), [R15-1219](#), [R15-1410](#), [R15-1411](#)).

Psoriasis Symptom Scale

Listed below are a set of problems that people with psoriasis have said are important. For each question, click on the circle that best describes the severity of your symptoms during the past 24 hours. Please answer every question.

Proprietary confidential information © 2017 Boehringer Ingelheim International GmbH or one or more of its affiliated companies

1. How severe was your pain from your psoriasis during the past 24 hours?
 - None
 - Mild
 - Moderate
 - Severe
 - Very severe
2. How severe was the redness from your psoriasis during the past 24 hours?
 - None
 - Mild
 - Moderate
 - Severe
 - Very severe
3. How severe was your itching from your psoriasis during the past 24 hours?
 - None
 - Mild
 - Moderate
 - Severe
 - Very severe
4. How severe was your burning from your psoriasis during the past 24 hours?
 - None
 - Mild
 - Moderate
 - Severe
 - Very severe

10.4.2 Dermatology Life Quality Index (DLQI)

The DLQI will be self-administered by the patient at visits indicated in the [Flow Chart](#).

The DLQI is a patient-administered, ten-question, quality of life questionnaire that covers six domains including symptoms and feelings, daily activities, leisure, work and school, personal relationships and treatment ([R05-2548](#)). The DLQI has a one-week recall period. Item scores range from 0 (not relevant) and 1 (not at all) to 3 (very much). Question 7 is a “yes”/“no” question where “yes” is scored as 3.

DLQI total score is calculated by summing the scores of each question resulting in a range of 0 to 30 where 0-1 = no effect on patient’s life, 2-5 = small effect, 6-10 = moderate effect, 11-20 = very large effect, and 21-30 = extremely large effect on patient’s life. The higher the score, the more the quality of life is impaired. A 5-point change from baseline is considered a clinically important difference.

The DLQI has been extensively used in clinical trials and has a large evidence base supporting reliability and validity ([R15-3845](#)).

DERMATOLOGY LIFE QUALITY INDEX

DLQI

Hospital No:

Date:

Name:

Score:

Address:

Diagnosis:

**The aim of this questionnaire is to measure how much your skin problem has affected your life
OVER THE LAST WEEK. Please tick one box for each question.**

1. Over the last week, how itchy, sore, painful or stinging has your skin been?	Very much 	A lot 	A little 	Not at all 	
2. Over the last week, how embarrassed or self conscious have you been because of your skin?	Very much 	A lot 	A little 	Not at all 	
3. Over the last week, how much has your skin interfered with you going shopping or looking after your home or garden ?	Very much 	A lot 	A little 	Not at all 	Not relevant 
4. Over the last week, how much has your skin influenced the clothes you wear?	Very much 	A lot 	A little 	Not at all 	Not relevant 
5. Over the last week, how much has your skin affected any social or leisure activities?	Very much 	A lot 	A little 	Not at all 	Not relevant 
6. Over the last week, how much has your skin made it difficult for you to do any sport ?	Very much 	A lot 	A little 	Not at all 	Not relevant 
7. Over the last week, has your skin prevented you from working or studying ?	Yes 	No 			Not relevant 
	A lot 	A little 	Not at all 		
8. Over the last week, how much has your skin created problems with your partner or any of your close friends or relatives ?	Very much 	A lot 	A little 	Not at all 	Not relevant 
9. Over the last week, how much has your skin caused any sexual difficulties ?	Very much 	A lot 	A little 	Not at all 	Not relevant 
10. Over the last week, how much of a problem has the treatment for your skin been, for example by making your home messy, or by taking up time?	Very much 	A lot 	A little 	Not at all 	Not relevant 

Please check you have answered EVERY question. Thank you.

©AY Finlay, GK Khan, April 1992 www.dermatology.org.uk, this must not be copied without the permission of the authors.

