5.1.3 Further Endpoints

The further endpoints are as follows:

- Achievement of $\geq 50\%$ reduction from baseline PASI score (PASI 50) at Weeks 16 and 52
- Time until the first achievement of PASI 50, PASI 75, PASI 90, PASI 100 and sPGA 0 or 1
- Time until loss of PASI 75, PASI 90, PASI 100 and sPGA 0 or 1 response
- Change from baseline in PASI score at Weeks 16 and 52
- Percent change from baseline in PASI at Weeks 16 and 52
- Absolute PASI of < 3 at all visits collected
- Achievement of an sPGA score of clear at Weeks 16 and 52
- Change from baseline in psoriasis symptoms evaluated using the total score on the Psoriasis Symptoms Scale (PSS) at Weeks 16 and 52
- Achievement of a Dermatology Life Quality Index (DLQI) score of 0 or 1 at Weeks 16 and 52
- Achievement of total score on the PSS of 0 at Weeks 16 and 52
- Change from baseline in DLQI at all Weeks 16 and 52

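### As written, the DLQI item scoring gives 1 point for 'not at all', so no completed questionnaire can total 0 or 1 and the DLQI 0/1 endpoint cannot be met in any arm

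*Protocol*

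**What the plan says.** Protocol 10.4.2 describes the instrument: "The DLQI is a patient-administered, ten-question, quality of life questionnaire". Its item rule is: "Item scores range from 0 (not relevant) and 1 (not at all) to 3 (very much"). A *yes* to question 7 scores 3. The ten items are then summed, "resulting in a range of 0 to 30 where 0-1 = no effect on" the patient's life. Totals of 2-5 count as a small effect and 6-10 as a moderate effect. The section takes a 5-point change from baseline as clinically important.

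The form follows in the same section. The questions that begin "1. Over the last week, how itchy, sore, painful or stinging has your skin been" and "2. Over the last week, how embarrassed or self conscious have you been because of your skin" offer four answers: very much, a lot, a little, not at all. Questions 3 to 10 also have a *not relevant* box. Question 7 is *yes* / *no* / *not relevant*, with a second row of *a lot*, *a little* and *not at all*.

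Protocol 5.1.3 lists this further endpoint: "Achievement of a Dermatology Life Quality Index (DLQI) score of 0 or 1 at Weeks 16 and 52". It also lists change from baseline in DLQI. SAP 10.3.1 carries both, at all visits collected. SAP 10.1.5 sets out item scores, total range and a missing-item rule for the PSS. The SAP has no counterpart for the DLQI.

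**The concern.** The item rule and the total-score rule stand next to each other and cannot both be true. If *not at all* is worth a point, a patient untroubled by the disease collects points on every graded item. The 0-1 band that defines both no effect and the responder endpoint is then out of reach.

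The item rule is also incomplete. The form has four ordered answers, but the values 1 to 3 leave room for only three distinct whole numbers. *A little* and *a lot* are given no score anywhere.

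Two listed endpoints depend on the scoring. The responder rate would be zero everywhere. Change from baseline would be measured on a compressed scale, and a patient who moves from *not relevant* to *not at all* would appear to worsen by a point. Under Protocol 3.1.1, data management, statistical evaluation and electronic outcome capture lie with different parties, so a correct written rule is needed.

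**Working it through.** **Inputs** (all from Protocol 10.4.2)
- Item scores as written: not relevant 0, not at all 1, very much 3; a little and a lot unstated.
- Ten items, summed; stated range 0 to 30.
- Questions 1-2: four answers, no *not relevant*. Questions 3-10: five possible outcomes each (question 7 taken as yes, a lot, a little, not at all, not relevant).

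**Step 1: try to reproduce the stated range.**
- Minimum = 2 items × 1 (questions 1-2, *not at all*) + 8 items × 0 (questions 3-10, *not relevant*) = 2.
- Maximum = 10 × 3 = 30.

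The rule gives 2 to 30, so the stated lower limit of 0 is not reproduced.

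**Step 2: count every complete response pattern.** There are 4² × 5⁸ = 16 × 390,625 = 6,250,000. Because two answers have no stated score, several values were tried.

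| Not at all | A little / a lot | Range of total | Patterns totalling 0 or 1 |
|---|---|---|---|
| 1 (as written) | 1 / 2 | 2 to 30 | 0 |
| 1 (as written) | 1.5 / 2 | 2 to 30 | 0 |
| 1 (as written) | 2 / 2 | 2 to 30 | 0 |
| 1 (as written) | 2 / 3 | 2 to 30 | 0 |
| 0 (corrected) | 1 / 2 | 0 to 30 | 1,792 |

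The last row can be checked by hand.
- Total 0: 2⁸ = 256 patterns (*not at all* or *not relevant* on each of questions 3-10).
- Total 1: 2 × 256 = 512 with *a little* on question 1 or 2, plus 8 × 2⁷ = 1,024 with *a little* on one of questions 3-10.
- Sum: 256 + 512 + 1,024 = 1,792.

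**Step 3: a patient with no impairment.**
- *Not at all* on the nine graded items, question 7 *no* taken as 0: 9 × 1 + 0 = 9.
- *Not at all* also on question 7's second row, scored 1: 10 × 1 = 10.

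Both lie in the 6-10 moderate-effect band. Under the corrected scoring both are 0.

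**Step 4: change from baseline.** A move from *very much* to *not at all* on all nine graded items is worth 9 × (3 − 1) = 18 points as written, against 9 × (3 − 0) = 27 as corrected. The 5-point threshold would be applied to the shorter scale.

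**Step 5: does missing-data handling create responders?** No, for wholly missing visits. Under Protocol 7.5 and SAP 10.1.4 a missing binary outcome counts as failure unless the visits before and after are both successes, and no visit can be a success.

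**Step 6: does the result depend on the form?** If *not relevant* were available on all ten items, a total of 0 or 1 would need at least nine *not relevant* answers: 1 + 10 = 11 of 5¹⁰ = 9,765,625 patterns, or 1 + 20 = 21 if *a little* also scored 1. The endpoint would still be practically unattainable.

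**The case against.** The best answer is that this is a wording slip that the section itself exposes. The 0 to 30 range and the 0-1 band show what was meant, and the section cites the instrument's source. The sentence cannot be programmed literally, because two answers have no score. A programmer would have to look further and would probably score the instrument properly, so 0% is what a literal reading gives and not a forecast of the trial's result. The stakes are also limited: the DLQI is a further endpoint, called exploratory in the SAP and outside the tested hierarchy, and no analysis by severity band is planned.

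Much of this stands. The harm is conditional on literal scoring, and the misclassification into the moderate band reaches no planned table. The figure for an unimpaired patient is 9 or 10, not a single number. Totals for partly completed questionnaires are undefined, because neither document gives a DLQI missing-item rule.

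It does not remove the point. The item rule is the only statement in either document of what each graded answer is worth, and it is wrong. Protocol 7.5 refers to the measure's instructions only for missing items, and the SAP adds nothing on DLQI items. Having to infer the scoring from a contradiction is a reason to correct the text.

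**Conclusion.** The point holds. Scored as written, the DLQI total runs from 2 to 30. No complete questionnaire can reach 0 or 1, and the DLQI 0/1 rate is 0% in every arm at every visit. An unimpaired patient scores 9 or 10 instead of 0.

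This rests on the printed form having no *not relevant* box on questions 1 and 2, and on complete questionnaires. It does not depend on the values given to *a little* and *a lot*, or on how question 7 is treated.

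The correction should be made, but it is not critical to the trial's conclusions: the primary and secondary endpoints, sample size and alpha are untouched.

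**What to change.** Replace the item-score sentence in Protocol 10.4.2 with: not at all = 0, not relevant = 0, a little = 1, a lot = 2, very much = 3. Keep question 7 *yes* = 3, and say that after a *no* the second-row answer is scored on the same scale. This gives each of the four ordered answers its own value, reproduces 0 to 30 and makes the 0-1 band attainable.

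Repeat the rule in the SAP next to the PSS scoring in 10.1.5, with a DLQI missing-item rule. Check whichever program computes the DLQI total against it, including the electronic device if it calculates scores.

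The cost is one sentence in the protocol appendix, a short entry in the SAP and one program check. No data collection changes.

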10.4.3 Health Assessment Questionnaire Disability Index (HAQ-DI)

The HAQ-DI will be self-administered by the patient at visits indicated in the [Flow Chart](#). The HAQ-DI is a twenty-item patient reported outcome instrument that assesses current physical function/disability. The HAQ-DI covers eight categories (dressing and grooming, hygiene, arising, reach, eating, grip, walking and common daily activities). There are four response options, ranging from 0 (no difficulty) to 3 (unable to do). HAQ-DI score is reported as a mean score between 0 and 3 by dividing the total score by the number of items answered ([R15-3849](#)).

The HAQ-DI has been the most-widely used instrument to assess physical function clinical trials of treatments for rheumatoid and psoriatic arthritis and has extensive evidence of its validity and other psychometric properties in this context ([R15-3846](#)).

The HAQ-DI will be self-administered by the patient at visits indicated in the Flow Chart.

HEALTH ASSESSMENT QUESTIONNAIRE

Name _____

Date _____

PATKEY# _____
QUESTDAT _____

In this section we are interested in learning how your illness affects your ability to function in daily life. Please feel free to add any comments on the back of this page.

HAQADMIN _____

Please check the response which best describes your usual abilities OVER THE PAST WEEK:

QUESTYPE _____

	Without ANY Difficulty	With SOME Difficulty	With MUCH Difficulty	UNABLE To Do
--	------------------------------	----------------------------	----------------------------	-----------------

DRESSING & GROOMING

Are you able to:

- Dress yourself, including tying shoelaces and doing buttons? _____
- Shampoo your hair? _____

PMSVIS _____
RASTUDY _____
QUESTNUM _____

DRESSNEW _____

ARISING

Are you able to:

- Stand up from a straight chair? _____
- Get in and out of bed? _____

RISENEW _____

EATING

Are you able to:

- Cut your meat? _____
- Lift a full cup or glass to your mouth? _____
- Open a new milk carton? _____

EATNEW _____

WALKING

Are you able to:

- Walk outdoors on flat ground? _____
- Climb up five steps? _____

WALKNEW _____

Please check any AIDS OR DEVICES that you usually use for any of these activities:

 Cane	 Devices used for dressing (button hook, zipper pull, long-handled shoe horn, etc.)
 Walker	 Built up or special utensils
 Crutches	 Special or built up chair
 Wheelchair	 Other (Specify: _____)

DRSGASST _____

RISEASST _____

Please check any categories for which you usually need HELP FROM ANOTHER PERSON:

 Dressing and Grooming	 Eating
 Arising	 Walking

EATASST _____

WALKASST _____

Proprietary confidential information © 2017 Boehringer Ingelheim International GmbH or one or more of its affiliated companies

Please check the response which best describes your usual abilities OVER THE PAST WEEK:

	Without ANY Difficulty	With SOME Difficulty	With MUCH Difficulty	UNABLE To Do	
HYGIENE					
Are you able to:					
- Wash and dry your body?	—	—	—	—	
- Take a tub bath?	—	—	—	—	
- Get on and off the toilet?	—	—	—	—	HYGNNEW_____
REACH					
Are you able to:					
- Reach and get down a 5 pound object (such as a bag of sugar) from just above your head?	—	—	—	—	
- Bend down to pick up clothing from the floor?	—	—	—	—	REACHNEW_____
GRIP					
Are you able to:					
- Open car doors?	—	—	—	—	
- Open jars which have been previously opened?	—	—	—	—	
- Turn faucets on and off?	—	—	—	—	GRIPNEW_____
ACTIVITIES					
Are you able to:					
- Run errands and shop?	—	—	—	—	
- Get in and out of a car?	—	—	—	—	
- Do chores such as vacuuming or yardwork?	—	—	—	—	ACTIVNEW_____
Please check any AIDS OR DEVICES that you usually use for any of these activities:					
 Raised toilet seat	 Bathtub bar				
 Bathtub seat	 Long-handled appliances for reach				
 Jar opener (for jars previously opened)	 Long-handled appliances in bathroom				
 Other (Specify: _____)					
Please check any categories for which you usually need HELP FROM ANOTHER PERSON:					
 Hygiene	 Gripping and opening things				
 Reach	 Errands and chores				
HYGNASST_____					
RCHASST_____					
GRIPASST_____					
ACTVASST_____					

10.4.4 pain VAS

The pain-VAS will be self-administered by the patient at visits indicated in the [Flow Chart](#). The patient's assessment of pain will be performed using a horizontal 100 mm VAS, ranging from 0 (no pain) to 100 (severe pain) after the question:
"Please indicate with a vertical mark (|) through the horizontal line the most pain you had from your psoriatic arthritis in the past week".

10.4.5 Patient's global assessment VAS

The patient global assessment VAS will be self-administered by the patient at visits indicated in the Chart. The patient's global assessment of disease activity will be performed using a horizontal 100 mm VAS, ranging from 0 (very well) to 100 (very poor) after the question:
"Considering all the ways psoriatic arthritis affects you, please indicate with a vertical mark (|) through the horizontal line how well you are doing in the past week".

11. DESCRIPTION OF GLOBAL AMENDMENT(S)

Number of global amendment	1.0
Date of CTP revision	08 Jun 2017
BI Trial number	1311.38
BI Investigational Product(s)	risankizumab, BI 655066
Title of protocol	A phase II/III, randomised, double-blind study to evaluate efficacy and safety of two different dose regimens of BI 655066 (risankizumab) and placebo and maintenance of response of BI 655066 (risankizumab) administered subcutaneously in Japanese patients with moderate to severe chronic plaque type psoriasis.
To be implemented only after approval of the IRB / IEC / Competent Authorities	
To be implemented immediately in order to eliminate hazard – IRB / IEC / Competent Authority to be notified of change with request for approval	
Can be implemented without IRB / IEC / Competent Authority approval as changes involve logistical or administrative aspects only	
Section to be changed	Protocol synopsis
Description of change	Changed multiple testing procedure
Rationale for change	To decrease type II error and newly planned procedure also controls family-wise type I error of less than 5%.
Section to be changed	Flowchart
Description of change	Added “X” for sPGA at Visit 1
Rationale for change	sPGA entry criteria collected on the electronic device was added to Flow Chart as a clarification
Section to be changed	Section 2.3
Description of change	Changed a item number
Rationale for change	To correct typo error
Section to be changed	Section 3.1.1
Description of change	Added text to specify Data Manage will be done by

Proprietary confidential information © 2017 Boehringer Ingelheim International GmbH or one or more of its affiliated companies

		BI and Statistical Evaluation will be done by AbbVie according to each SOPs.
Rationale for change		In February 2016, AbbVie entered into a license agreement with BI related to risankizumab, and in October 2016, the US IND for risankizumab transitioned from BI to AbbVie. To modify study conduct responsibilities as a result of that license agreement.
Section to be changed		Section 3.3.4.2
Description of change		Updated text to “BI/AbbVie reserves the right to discontinue the trial overall or at a particular trial site at any time for the following reasons”.
Rationale for change		In February 2016, AbbVie entered into a license agreement with BI related to risankizumab, and in October 2016, the US IND for risankizumab transitioned from BI to AbbVie. To modify study conduct responsibilities as a result of that license agreement.
Section to be changed		Table 4.2.2.1: 1
Description of change		Changed a rank of topical steroid from “mild” to “medium”
Rationale for change		To correct description
Section to be changed		Section 5.5.3.2
Description of change		Specified DNA banking sample storage
Rationale for change		In February 2016, AbbVie entered into a license agreement with BI related to risankizumab, and in October 2016, the US IND for risankizumab transitioned from BI to AbbVie. To modify study conduct responsibilities as a result of that license agreement.
Section to be changed		Section 7.2
Description of change		Changed multiple testing procedure
Rationale for change		To decrease type II error and newly planned procedure also controls family-wise type I error of less than 5%.
Section to be changed		Section 7.3
Description of change		Changed analysis populations : FAS to ITT Population SAF to Safety Population PPS to PP Population
Rationale for change		All changes were made under blinding prior Data

		base lock. FAS to ITT Population: ITT analysis is more conservative approach. SAF to Safety Population: Terminology changes PPS to PP Population: New definition is based on more concrete definition.
Section to be changed		Section 7.3.1
Description of change		Changed confidence interval
Rationale for change		It corresponds to changes in 7.2.
Section to be changed		Section 7.3.3
Description of change		Corrected typo Changed Definition of Loss of Endpoint
Rationale for change		To correspond to changes in 7.3 and it was based on ITT principle.
Section to be changed		Section 7.3.4
Description of change		Changed text to specify that AbbVie summary tables and listings will be produced and analyses based on AbbVie standards
Rationale for change		In February 2016, AbbVie entered into a license agreement with BI related to risankizumab, and in October 2016, the US IND for risankizumab transitioned from BI to AbbVie. To modify study conduct responsibilities as a result of that license agreement.
Section to be changed		Section 7.5
Description of change		Changed missing data handling
Rationale for change		To correspond to changes in 7.3 and it was based on ITT principle.
Section to be changed		Section 7.7

3.0 Introduction

This Statistical Analysis Plan (SAP) describes the statistical analysis to be completed by the AbbVie Clinical Statistics Department for risankizumab study Protocol M16-004 (BI Study 1311.38) dated 05 September 2016 and the protocol amendment dated 07 June 2017.

This SAP will provide details to further elaborate statistical methods as outlined in the Protocol of Study 1311.38.

Analyses will be performed using SAS® version 9.4 (SAS Institute, Inc., Cary, NC 27513) or higher using the UNIX operating system.

SAP will not be updated in case of future administrative or minor amendments to the protocol unless the changes have any impact on the analysis of the study data.

4.0 Study Objectives, Design and Procedures

4.1 Objectives

The objectives of this study are to assess the efficacy and safety of two different dose regimens of risankizumab compared to placebo in patients with moderate to severe chronic plaque psoriasis. The primary efficacy evaluation will be performed at Week 16 and an assessment of maintenance of response will be performed at Week 52.

In the subset of enrolled patients with concomitant psoriatic arthritis, the signs and symptoms of psoriatic arthritis will be evaluated to assess improvement during the trial.

This trial will assess PK and the emergence of anti-drug antibodies (ADA) and their effect on efficacy and safety. Moreover, it will be explored how the use of risankizumab may influence protein expression levels and disease specific protein markers. These analyses will not be covered in this SAP.

